#### 7.12.3 Vital Signs, Height, Weight, and Body Mass Index

Observed values and change from baseline for each parameter of continuous vital sign parameters (blood pressure, temperature, pulse rate and respiratory rate) and height, weight, and BMI will be summarized by overall treatment and visit using descriptive statistics.

All vital signs and height, weight, and BMI data will be listed individually by each subject. Abnormal values will be flagged in the listing.

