shorter than 28 days as patients who meet study entry criteria will be eligible to receive the investigational product on the 6th day after completing all screening procedures and assessments. At the Screening Period visit (Visit 1), the investigator will ensure that the patient's legal representative (parent[s]/caregiver[s]) provides a written informed consent form (ICF) on behalf of the infant patient. Patient's parent(s)/caregiver(s) will receive a copy of the ICF for review and must provide the ICF prior to study participation. A 16-hour, video-EEG will be completed within the Screening Period (overnight video-EEG). Seizure diary will be distributed on the Screening Period visit (Visit 1) and families will be trained by the investigator or his/her delegate on how to log seizures. Patients will be allowed to be re-screened once with the approval of the medical monitor or sponsor.

Treatment Period 1 (Days 1 to 28):

Patients will report to the hospital/clinic on Day 1 (Visit 2) and will remain at the clinical site for the first 24 hours following the first dose of investigational product. During Day 1 (Visit 2), vital signs will be monitored. The first 2 doses of the investigational product (6 mg/kg orally) will be administered during Visit 2. Physical and neurological examinations will occur prior to the first dose on Day 1, and on Day 2 prior to discharge. The investigator or his/her delegate will contact the parent/caregiver by telephone or email during the next 5 days (from Day 2 to 6) of Treatment Period 1 to ensure that the seizure diary is being completed, to review seizure counts, and to conduct daily assessments which includes following questions:

- Have you noticed any change in seizure pattern?
- Have you noticed an evolution of new seizure type?
- Have you noticed any changes in appetite?
- Have you noticed a change in stools?
- Have you noticed excessive sedation?
- Have you noticed excessive irritability?
- Have you noticed the onset of new rash?

- Has your child experienced any possible AE?
- Did your child take all prescribed doses of the investigational product today?
- Did your child take all prescribed doses of other drugs used for treating epileptic seizures today?
- Did your child require the use of a rescue medication for the treatment of a breakthrough seizure today?
- What, if any, prescribed or over-the-counter medications is your child currently taking?

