4.1.1 Inclusion Criteria

Each patient must meet all the following criteria to be enrolled in this study:

1. Parent(s)/caregiver(s) fully comprehend and sign the ICF in accordance with applicable laws, regulations, and local requirements, understand all study procedures, and can communicate satisfactorily with the investigator and study coordinator.
2. Is a male or female from 6 months through 36 months of age at the time of informed consent.
3. Has clinical diagnosis of IS, confirmed by video-EEG analysis, and hypsarrhythmia on EEG at screening according to the Burden of Amplitudes and Epileptiform Discharges (BASED) scale score.
4. As assessed by the investigator, has no or partial response to at least 2 out of the 3 therapies of ACTH, vigabatrin, and glucocorticoids (i.e. prednisolone), or has no or partial response to at least 1 out of the 3 therapies of ACTH, vigabatrin, and glucocorticoids and is contraindicated to and/or refused by the patient's legal representative(s) for treatment with 1 or both other 2 therapies.

5. Has general good health (defined as the absence of any clinically relevant abnormalities as determined by the investigator) based on physical and neurological examinations, medical history, normal renal function, and ECG, and clinical laboratory values completed during the Screening Period visit (Visit 1).
6. Parent(s)/caregiver(s) is willing and able to comply with the study procedures and visit schedules in the opinion of the investigator.

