7.7.1 Analysis of Primary Safety Endpoint

Investigational Product Administration and Exposure: Investigational product administration and exposure will be summarized and listed. Further details on the investigational product administration and exposure calculation will be given in the SAP.

Medical History: Medical history details recorded at screening will be summarized and listed according to the coded MedDRA (latest version) by system organ class (SOC) and preferred term (PT).

Prior and Concomitant Medications: Prior and concomitant medications will be summarized according to the World Health Organization Drug Dictionary (WHODrug). The number and percentage of patients will be presented for previous and concomitant medications.

Adverse Events: AEs will be coded according to the coded MedDRA (latest version). Treatment-emergent AEs will be tabulated by SOC and PT. The following summary tables will be produced:

- TEAEs
- Treatment-related TEAEs
- TEAEs leading to investigational product discontinuation
- Treatment-related TEAEs leading to investigational product discontinuation

- Serious TEAEs
- Treatment-related serious TEAEs
- TEAEs leading to death
- Treatment-related TEAEs leading to death.

All AEs recorded during the study (including non-treatment-emergent AEs) will be listed.

Physical and Neurological Examination: Descriptive summaries of change in examination findings from baseline to post-baseline visits will be presented by test in a shift table (normal, abnormal [not clinically significant], and abnormal [clinically significant]).

Vital Signs: Descriptive by-visit summaries of vital signs data will be presented (including raw values and change from baseline). Vital signs will include blood pressures, temperature, pulse rate, and respiratory rate.

Height, Weight, and BMI: Baseline height, weight, and BMI will be summarized and listed.

ECGs: Descriptive summaries of change in overall assessment from baseline to post-baseline visits will be presented in a shift table (normal, abnormal [not clinically significant], and abnormal [clinically significant]). In addition, descriptive by-visit summaries of ECG data will be presented (including raw values and change from baseline). ECG data will include all of the following intervals: RR interval, PR interval, QRS width, QT interval, and QT interval from Fridericia's formula (QTcF).

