## 7 STATISTICAL METHODS

### 7.1 General

All statistical analysis will be conducted following the principles specified in the International Conference on Harmonization (ICH) Topic E9 Statistical Principles for Clinical Trials (CPMP/ICH/363/96).

All statistical analyses will be performed using the statistical software SAS, Version 9.4 or newer and any exceptions will be detailed in the CSR.

All results collected in the database will be presented in listings. Both absolute values and change-from-baseline values for each subject will be given where applicable. All continuous data will be listed with the same precision as presented in the database. Data listings will be sorted by subject ID, and time point.

Unless otherwise noted, continuous variables will be summarized using the number of non-missing observations (n), arithmetic mean (mean), standard deviation (SD), median, minimum, maximum, Quartile 1 (Q1), and Quartile 3 (Q3); categorical variables will be summarized using the frequency count and the percentage of subjects in each category. Time to event data will be summarized using median, 25%, and 75% percentiles.

In the data listings, study day relative to first dose of treatment may be presented. Study day relative to first dose will be calculated as: event date – first dose date (+1 if event date  $\geq$  first dose date).

Baseline will be the last non-missing available measurement prior to first dose of the study drug.

For safety summaries, the unscheduled and repeat assessments will not be summarized; however, all results will be included in the data listings.

All PK parameters will be summarized by the overall treatment group using descriptive statistics to include, as appropriate, n, mean, SD, coefficient of variation (CV), minimum, median, maximum, geometric mean (GM), and geometric CV.

Disposition, demographics and baseline characteristics, all safety parameters and adverse events will be summarized overall.

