Table 14.3.1.4	Summary of TEAEs Leading to Investigational Product Discontinuation by System Organ Class and Preferred Term (Safety Population)
Table 14.3.1.5	Summary of Treatment-Related TEAEs leading to investigational product discontinuation by System Organ Class and Preferred Term (Safety Population)
Table 14.3.1.6	Summary of Serious TEAEs by System Organ Class and Preferred Term (Safety Population)
Table 14.3.1.7	Summary of Treatment-Related Serious TEAEs by System Organ Class and Preferred Term (Safety Population)

Table 14.3.1.8	Summary of TEAEs Leading to Death by System Organ Class and Preferred Term (Safety Population)
Table 14.3.1.9	Summary of Treatment-related TEAEs Leading to Death by System Organ Class and Preferred Term (Safety Population)
Section 14.3.2	Listings of Deaths, Other Serious and Certain Significant Adverse Events
Table 14.3.2.1	Listing of Deaths, Other Serious Adverse Events, and Significant Adverse Events (Safety Population)
Section 14.3.4	Laboratory Summaries
Table 14.3.4.1	Listing of Abnormal Laboratory Results (Safety Population)
Table 14.3.4.2	Observed and Change from Baseline for Clinical Laboratory Parameters (Safety Population)
Table 14.3.4.3	Shift Assessment of Categorical Change of Laboratory Results from Baseline to each Post-Baseline Visit (Safety Population)
Section 14.3.5	Additional Safety Data Summaries
Table 14.3.5.1	Observed and Change from Baseline Vital Signs, Height, Weight, and Body Mass Index (Safety Population)
Table 14.3.5.2	Observed and Change from Baseline ECG (Safety Population)
Table 14.3.5.3	Shift Assessment of Overall ECG Interpretation at Baseline and Each Post-Baseline Time-point (Safety Population)
Table 14.3.5.4	Shift Assessment of Physical and Neurological Examination at Baseline and Each Post-Baseline Time-point (Safety Population)
Table 14.3.5.5	Summary of COVID-19 Data (Safety Population)
Listing Number	Listing Name
Section 16.2.1	Discontinued Subjects
Listing 16.2.1	Subject Disposition (All Enrolled Population)
Section 16.2.2	Protocol Deviations

---

Listing 16.2.2	Protocol Deviations (Safety Population)
Section 16.2.3	Subjects Excluded from Analysis
Listing 16.2.3	Exclusions from Analysis Populations (All Enrolled Population)
Section 16.2.4	Demographic Data
Listing 16.2.4.1	Demographics and Baseline Characteristics (Safety Population)

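### Weight, height and BMI are summarised as raw change from baseline in growing children with no control arm, so expected growth can hide poor weight gain; age- and sex-standardised scores should sit beside the raw values

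*SAP*

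**What the plan says.** The governing sentence in SAP 7.12.3 opens with "Observed values and change from baseline for each parameter of continuous vital sign parameters" and ends by stating that "height, weight, and BMI will be summarized by overall treatment and visit using descriptive statistics". The title of Table 14.3.5.1 in SAP section 8 confirms that change from baseline applies to height, weight and BMI, in the Safety Population.

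Other relevant provisions:

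- Baseline (SAP 7.1): "Baseline will be the last non-missing available measurement prior to first dose of the study drug". Nothing adjusts for growth after that point.
- Population (Protocol 4.1.1): "Is a male or female from 6 months through 36 months of age at the time of informed consent".
- Schedule (Protocol 6.1.2 and Table 13-1): height, weight and BMI at each clinic visit, that is Screening and Days 1, 7, 21, 28, 42 and 56.
- Only other provision for these measures in SAP 7.12.3: individual listings, with "Abnormal values will be flagged in the listing". No criterion for an abnormal weight, height or BMI is given.
- Protocol 7.7.1, on the same data: "Baseline height, weight, and BMI will be summarized and listed". The SAP goes further than this, although SAP section 4 reports no change from the protocol.

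Neither document mentions a z-score, centile or growth standard.

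**The concern.** Children of this age are expected to gain weight and length during the study, at rates that depend on age and sex. A single-arm study has no concurrent group to show what that gain would have been. A mean change near zero, or slightly positive, can look harmless in the planned table when it reflects poor growth. In the other direction, ordinary growth would be added to any drug-related weight gain.

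Pooling adds to the difficulty. Only 7 of about 35 enrolled children must be 6 to 12 months old, so the age mix, and with it the expected mean gain, is not known in advance. SAP 7.2 does not impute missing data, so the mix can also shift between visits.

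Safety and tolerability are the primary objective, and Protocol 6.1 lists height, weight and BMI among the safety variables. The telephone script in Protocol 3.1 asks "Have you noticed any changes in appetite". Protocol 5.1 requires a fast of at least 2 hours before each of two daily doses and allows food 2 hours afterwards. Weight is thus a natural outcome to be able to read. What is at stake is the interpretation of one descriptive safety table.

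**Working it through.** The documents give no growth figure, so there is no stated number to reproduce. The check is an illustration for weight only; no inputs are assumed for height or BMI.

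**Model.** Let G(t) be the expected gain from first dose to time t, d the deficit and SD_ref the reference SD for age and sex.

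- Raw mean change = G(t) − d
- Change in z ≈ −d / SD_ref

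**Inputs.**

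| Input | Value | Source |
|---|---|---|
| Expected gain over 56 days | 0.3 to 0.8 kg | assumption |
| SD_ref | 0.9 to 1.5 kg | assumption |
| SD of individual change | 0.2 to 0.4 kg | assumption |
| Number of children | 26 to 35 | target completers and enrolment, Protocol 7.4 |
| End of full dosing | Day 28 | Protocol 3.1 |
| Dose halved; halved again; stopped | Day 29; Day 35; Day 42 | Protocol 3.1 |

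**Step 1. Expected gain by Day 28,** pro rata: 0.3 × 28/56 = 0.15 kg, to 0.8 × 28/56 = 0.40 kg.

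**Step 2. Complete arrest to Day 28 (d = G).** Raw change = 0 kg. Fall in z = 0.15/1.5 = 0.10, to 0.40/0.9 = 0.44.

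**Step 3. Halved gain to Day 28 (d = G/2).** Raw change = +0.15/2 = +0.075 kg, to +0.40/2 = +0.20 kg. The table would report a gain in either case.

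**Step 4. Sampling error of the mean.** The 95% half-width is 1.96 × SD/√n. It runs from 1.96 × 0.2/√35 = 0.07 kg to 1.96 × 0.4/√26 = 0.15 kg. The slow-growth figures (0.15 kg for arrest, 0.075 kg for halved gain) fall within that range. The fast-growth figures (0.40 and 0.20 kg) exceed it.

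**Step 5. Sensitivity.** A second assumed set, 0.15 to 0.50 kg per 30 days over the 27 days from Day 1 to Day 28 with SD_ref 1.0 to 1.5 kg, gives an expected gain of 0.15 × 27/30 = 0.135 kg to 0.50 × 27/30 = 0.45 kg. Arrest then means a fall of 0.135/1.5 = 0.09 to 0.45/1.0 = 0.45 z, and halved gain shows +0.07 to +0.23 kg. The conclusion is unchanged.

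**Step 6. Would a fixed cut-off serve?** On the main inputs, complete arrest to Day 28 produces a fall of at most 0.44 z. A rule of 0.5 z or more would not flag such a child. A count of absolute weight loss also misses arrest, because the change is exactly 0. Hence the distribution of z change is needed.

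**The case against.** **Partial safeguards exist.** SAP 7.1 reports minimum, Q1 and median, so the table will show whether any child lost weight. Every child's values are listed. Adverse events are to be identified from any study data, and a DSMB meets after 5, 10, 20 and 30 children have completed Treatment Period 1. SAP 7.3 plans age-band summaries for the primary safety endpoints. These help with individual children, but none removes expected growth. Raw change within an age band still contains it, weight is not named in SAP 2.4.1, and the abnormal flag has no criterion.

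**Standardised scores would not isolate a drug effect.** This stands. The children are refractory, with earlier ACTH, vigabatrin or steroids, and Protocol 1.2 itself reports obesity and growth retardation with ACTH. Some are tube-dosed if the option in Protocol 5.2 is used. A general growth standard is not their natural trajectory.

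**Stronger readings that the documents do not support:**

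- A reader might project the deficit over all 56 days (0.3/1.5 = 0.20 to 0.8/0.9 = 0.89 z). The 15 mg/kg dose runs only from Day 15 to Day 28, tapering follows, and the product stops on Day 42. Day 28 is the fairer anchor, and even that assumes arrest from first dose.
- A reader might say that growth simply masks a drug effect. It can hide a negative effect, but it would exaggerate a positive one.
- A reader might take appetite to be an identified risk with weight as its only objective measure. It is one of twelve routine questions and asks about change in either direction. Albumin, total protein, glucose and urine ketones are also collected.

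**Conclusion.** The point holds as a modest improvement. With no control arm and no growth reference, the planned mean change contains an unknown expected gain and cannot by itself show reduced weight gain. On the assumed inputs, complete arrest to Day 28 reads as 0 kg in place of a fall of about 0.10 to 0.44 z, and halved gain reads as about +0.08 to +0.20 kg. At slow growth the signal is about the size of sampling error, so standardising the scores makes the table interpretable without guaranteeing that an effect would be seen. All growth figures are assumptions, growth is taken as linear over the period, and SD_ref as constant.

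The analysis of TEAE incidence is unaffected, and Protocol 7.7 plans no formal testing. It would be too much to infer that the study will conceal harm, or that z-scores would attribute a change to the drug. The SAP already accepts age-banded safety criteria for ECG intervals in 7.12.4; growth is the comparable case left without them.

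**What to change.** In SAP 7.12.3 and Table 14.3.5.1, keep the raw values and add:

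- weight-for-age, length/height-for-age and weight-for-length (or BMI-for-age) z-scores from one named growth standard, using sex and age at each visit;
- change in z-score by visit, at least for Days 28, 42 and 56, with a descriptive 95% CI;
- the distribution of z change in place of a fixed cut-off such as 0.5 z;
- the number of children with any absolute weight loss;
- a stated criterion for the abnormal flag on weight, height and BMI;
- a sentence saying that the scores remove only reference-population growth, and not confounding by disease, earlier ACTH or steroids, or concomitant drugs.

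In the same edit, reconcile the baseline-only summary in Protocol 7.7.1 with the by-visit summary in the SAP.

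**Cost.** Some programming and extra rows in one table. Sex, age, height, weight and visit timing are already collected. Three things need checking: that age at each visit can be derived precisely enough (date of birth is not mentioned), whether length is measured lying or standing, and whether gestational age is available. The documents are silent on the last two. The downside is that results depend on the chosen standard, so it should be fixed before database lock.

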#### 7.12.4 Electrocardiograms

Continuous ECG parameters including RR interval, PR interval, QRS width, QT interval, and QTcF interval will be summarized by overall treatment and scheduled timepoints in terms of absolute values and change from baseline using descriptive statistics.

Shift tables will be presented that summarize the overall ECG interpretation as normal, abnormal not clinically significant, or abnormal clinically significant at baseline and each post-baseline time point.

ECG data will be listed by subject at each visit and time point collected with indicated clinically significant results.

ECG results meeting pre-specified criteria are listed and summarized. The following reference range ECG criteria by age range will be used.

Age Range	ECG Parameters	Lower Limit of Normal	Upper Limit of Normal
6-12 Months (including 12 th Month)	QT Interval	381 msec	449 msec
	QTcF Interval	350 msec	440 msec
>12-24 Months	QT Interval	381 msec	455 msec
	QTcF Interval	350 msec	440 msec
>24-36 Months	QT Interval	381 msec	455 msec
	QTcF Interval	350 msec	440 msec

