### 3.8.4 Electrocardiograms

The 12-lead ECG will be measured at following time points: Screening, Treatment Period 1 on Day 7 and 28, and Treatment Period 2 on Day 42.

ECG parameters will include RR interval, PR interval, QRS width, QT interval, and QT interval from Fridericia's formula (QTcF). Subjects with ECG assessments will be interpreted locally and will include comments on whether the tracings are normal or abnormal; rhythm, presence of arrhythmia or conduction defects; morphology, any evidence of myocardial infarction, or ST segment, T Wave, and U Wave abnormalities.

The investigator will determine whether any of the 12-lead ECG results are normal or abnormal, and if abnormal results are clinically significant or not clinically significant. Clinical significance

is defined as any variation in results that has medical relevance and may result in an alteration in medical care (e.g., active observation, diagnostic measures, or therapeutic measures). If a clinically significant change from screening values is noted, the clinically significant value and reason for clinical significance will be documented on the AE page of the patient's eCRF and a pediatric cardiology consultation will be prompted.

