#### 7.12.2 Clinical Laboratory Assessments

Observed values and change from baseline for each parameter of continuous clinical laboratory values (hematology, coagulation, serum chemistry and urinalysis) will be summarized by overall and visit using descriptive statistics.

Shift from screening/baseline to post-baseline laboratory findings in normal range criteria will also be summarized.

A listing of all clinical laboratory data for each subject at each visit will be presented. Clinical laboratory values that are outside the normal ranges will be presented in a separate listing. The normal ranges will also be listed.

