## **Section 16.2.8**

### **Individual Laboratory Measurements by Subject**

- Listing 16.2.8.1 Normal Ranges for Laboratory Data
- Listing 16.2.8.2 Clinical Laboratory Data by Category (Safety Population)
- Listing 16.2.8.3.1 Vital Signs (Safety Population)
- Listing 16.2.8.3.2 Weight, Height and BMI (Safety Population)
- Listing 16.2.8.4 Electrocardiogram Results (Safety Population)
- Listing 16.2.8.5 Electrocardiogram Results Meeting Prespecified Criteria (Safety Population)
- Listing 16.2.8.6 Physical and Neurological Examination Findings (Safety Population)
- Listing 16.2.8.7 COVID-19 Data (Safety Population)

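### The SAP's raw QT limits of normal (381 to 449 or 455 msec) conflict with its QTcF limits (350 to 440 msec): above about 92.4 bpm no ECG can be in range on both

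*SAP*

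**What the plan says.** SAP 7.12.4 (Electrocardiograms) states that "ECG results meeting pre-specified criteria are listed and summarized" and then that "The following reference range ECG criteria by age range will be used". The table has columns for the lower and upper limit of normal:

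| Age band | Raw QT (msec) | QTcF (msec) |
|---|---|---|
| 6-12 months | 381 to 449 | 350 to 440 |
| >12-24 months | 381 to 455 | 350 to 440 |
| >24-36 months | 381 to 455 | 350 to 440 |

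No heart-rate basis is given for the raw QT limits, no source for either row, and no rule for which row takes precedence. SAP 3.8.4 and Protocol 7.7.1 identify QTcF as the Fridericia correction, and both QT and RR are collected.

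The only output in SAP section 8 built on these limits is Listing 16.2.8.5, whose title begins "Electrocardiogram Results Meeting Prespecified Criteria (Safety Population". Section 8 contains no table for the promised summary.

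**The concern.** Raw QT and QTcF are tied together by heart rate, so fixed limits on both imply a range of rates over which an ECG can be normal on both. Here the raw QT range lies above the QTcF range at each end (381 against 350, and 449 or 455 against 440). Under Fridericia, raw QT exceeds QTcF only when RR is longer than 1 second, that is, below 60 bpm. Nothing in the documents explains why the limits should be ordered this way for children of 6 to 36 months.

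ECGs are among the primary safety endpoints (SAP 2.4.1). If the raw QT limits cannot be met at the rates the trial records, the criteria listing fills with QT-below-normal entries for ECGs whose QTcF is in range, and being listed tells the reader little.

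SAP 7.12.4 does not say outright that results outside the limits are the ones listed. The column headings point that way, and so does the parallel laboratory rule in SAP 7.12.2: "Clinical laboratory values that are outside the normal ranges will be presented in a separate listing". If the criteria instead meant in range on both rows, no ECG above the critical rate could qualify.

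**Working it through.** **Inputs.** The limits are those in SAP 7.12.4. The documents name Fridericia's formula but do not write it out; it is QTcF = QT / RR^(1/3), with RR in seconds and heart rate (HR) = 60/RR. The documents give no heart rates, so 80 to 160 bpm is an assumed range.

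**Highest rate at which both rows can be met.** This needs QT >= 381 and QT / RR^(1/3) <= 440, so:

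- RR >= (381/440)^3 = 0.6493 s
- HR <= 60 / 0.6493 = 92.41 bpm

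The result is the same in all three age bands, because 381 and 440 do not change with age. Rounding to whole milliseconds moves it only to between 92.7 and 93.1 bpm.

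**The rows at each rate** (msec):

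| HR (bpm) | Raw QT equivalent to QTcF 350 to 440 | QTcF at QT 381 | QTcF at QT 449 / 455 |
|---|---|---|---|
| 80 | 318.0 to 399.8 | 419.3 | 494.2 / 500.8 |
| 90 | 305.8 to 384.4 | 436.1 | 514.0 / 520.8 |
| 100 | 295.2 to 371.1 | 451.7 | 532.3 / 539.5 |
| 120 | 277.8 to 349.2 | 480.0 | 565.7 / 573.3 |
| 140 | 263.9 to 331.7 | 505.3 | 595.5 / 603.5 |
| 160 | 252.4 to 317.3 | 528.3 | 622.6 / 631.0 |

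From 100 bpm upward, the whole in-range QTcF interval corresponds to raw QT below 381 msec, and the whole in-range QT interval corresponds to QTcF above 440 msec.

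**Overlap at or below 92.4 bpm.** The part of the 90 msec QTcF span (440 - 350) that is also in range on raw QT is:

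- 80 bpm: (440 - 419.3)/90 = 23.0%
- 85 bpm: (440 - 427.9)/90 = 13.4%
- 90 bpm: (440 - 436.1)/90 = 4.3%

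These are shares of the interval, not of patients or ECGs.

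**What the raw QT upper limit adds.** A QT above the upper limit already implies QTcF above 440 msec whenever HR exceeds:

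- 60 / (449/440)^3 = 56.5 bpm for the 449 msec limit
- 60 / (455/440)^3 = 54.3 bpm for the 455 msec limit

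Above those rates it flags nothing that the QTcF row does not.

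**Number of ECGs.** SAP 3.8.4 schedules ECGs at "Screening, Treatment Period 1 on Day 7 and 28, and Treatment Period 2 on Day 42", Protocol 6.1.3 specifies single ECGs, and Protocol 4.2.3 closes enrolment once 35 patients have begun treatment. That gives 35 x 4 = 140 scheduled ECGs, of which 35 x 3 = 105 are post-baseline.

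**The case against.** The arithmetic is not in dispute. The strongest reply is that the rows limit two different quantities, and the SAP never requires an ECG to be in range on both. Overall normality is the investigator's interpretation, not a product of this table. At or below 92.4 bpm the rows can both be met, and neither need be a misprint: they may come from different sources or rate conditions. A listing set out by parameter would still separate QTcF above 440 msec from QT below 381 msec, so no prolonged QTcF would be missed. The out-of-range reading is partly inferred from a laboratory section. Dropping the raw QT rows would also favour one row when the documents do not show which is at fault.

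Much of this stands, and it is why the point is minor. The number of ECGs affected is unknown. The figure of 140 counts scheduled ECGs only: other sections give enrolment as approximately 35, and SAP 7.1 also sends unscheduled and repeat results to the listings.

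It does not remove the conflict. Followed exactly, the table still puts every ECG above 92.4 bpm into the listing on at least one row, and nothing in the SAP states a rate basis under which the raw QT limits would make sense. Separating entries by parameter lets the reader set the low-QT entries aside, but does not make them informative. Reporting raw QT descriptively is only a fallback for when the source cannot be traced.

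**Conclusion.** The concern holds, as a minor point. The SAP's two sets of limits cannot both be met above about 92.4 bpm in any age band. That figure follows from the SAP's own limits and Fridericia's formula and needs no further assumption.

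The practical effect rests on two things. One is that results outside the limits are what is listed. The other is the heart rates recorded, which the documents do not give. Within the assumed 80 to 160 bpm, the effect runs from partial overlap (23% of the QTcF span at 80 bpm) to none above 92.4 bpm.

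The reach is small. It covers Listing 16.2.8.5 and the untabled summary. The QTcF row still captures every value above 440 msec. Table 14.3.5.2 ("Observed and Change from Baseline ECG (Safety Population"), Table 14.3.5.3 (the shift in overall ECG interpretation) and the investigator's assessment of clinical significance do not use the limits. TEAE incidence does not depend on them directly. The documents do not show which row, if either, is misstated.

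**What to change.** Before the outputs are programmed:

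1. Check both rows against their source, reconcile them, and state in SAP 7.12.4 the heart-rate basis of the raw QT limits.
2. If they cannot be reconciled, take the raw QT rows out of the criteria listing and report raw QT descriptively, as Table 14.3.5.2 already does.
3. State explicitly that a result is listed when it falls outside the limits, if that is the intention.
4. As housekeeping, add the promised criteria summary to section 8 or delete the reference to it in 7.12.4.

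No new limit is proposed here. The cost is one table edit, a clarifying sentence and at most one line in the output list. No new data are needed: RR, QT and QTcF are already collected, so the sponsor can count the ECGs with RR below 0.649 s and see how many are affected.
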